6.4. Follow-up for Late Immune-related Adverse Events

Patients will undergo telephone follow-ups at 90 and 120 day (± 7 days) after the last dose of study drug to assess potential late irAEs. If any concern arises, patient will be called in for an inpatient follow up visit within 5 calendar days of initial phone call. For this inpatient follow-up visit, the [Schedule Of Activities](#) will be similar to the 1-month follow-up visit completed after EOT.

Patients continuing to experience late immune-related toxicity at this point (up to 120 days after last dose of study drug) will continue to be followed at least every 4 weeks until resolution or determination, in the clinical judgment of the investigator, that no further improvement is expected.

6.5. Survival Follow-up

To collect OS data, patients will be contacted by telephone every 8 weeks (± 7 days) post 120 day follow up visit, until end of the trial (2 years after last patient first dose). If the patient is seen in the clinic during the window of time that a scheduled telephone call is to be made to collect survival data, then the clinic visit may replace the survival telephone call. After the completion of the EOT visit subsequent anti-cancer therapy will be documented and recorded for patients who discontinue investigational products and continue in 120 day safety follow-up, and subsequently during survival follow-up.

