Protocol Activity	Screening ^a (≤28 days prior to study entry)	Day 1	Day 8	Day 15	Day 22	Day 1	Day 1		28 days	90 days	120 days	Every 2 months after 120 day follow up visit
Visit Window			±1	±2	±2	±2	±2		±7	±7	±7	±7
Informed Consent ^b	X											
Tumor History ^c	X											
Medical History ^d	X											
Complete Physical Examination	X	X						X	X			
Abbreviated Physical Examination ^e			X	X	X	X	X					
Baseline Signs and Symptoms ^f		X										
Height	X											
Weight ^g	X	X				X	X	X				
Vital Signs (BP/pulse rate/PO/Temp) ^h	X	X	X	X	X	X	X	X	X			
ECOG Performance Status ⁱ	X	X				X	X	X	X			
Triplicate 12-Lead ECG ^j	X (single ECG only)	X	X			X	X	X				

Schedule of Activities for Part 2 SC Administration of PF-06801591		Treatment Period						EOT ^{bb}	Post-Treatment				
		Cycle 1 Only (Days 1 to 28)				Cycle 2 (Days 1 to 28)	Subsequent Cycles (Days 1 to 28) ^{aa}		1-Month and Late irAE Follow up ^{cc}			Survival Follow Up ^{dd}	
Protocol Activity	Screening ^a (≤28 days prior to study entry)	Day 1	Day 8	Day 15	Day 22	Day 1	Day 1		28 days	90 days	120 days	Every 2 months after 120 day follow up visit	
Laboratory													
Hematology ^k	X	X	X	X	X	X	X	X	X				
Blood Chemistry ^l	X	X	X	X	X	X	X	X	X				
Coagulation ^m	X	X	X	X	X	X	X	X	X				
Urinalysis ⁿ	X			X		X	X	X	X				
Pregnancy Test or FSH Level ^o	X	X				X	X	X	X				
Pregnancy Test or FSH Level in Post-Treatment Follow-up (Specific for Poland only) ^o									(Days)				
									28	60	90	120	150
									X	X	X	X	X
CCI													
Hepatitis B, C, and HIV tests ^q	X												
Registration and Treatment													
Registration ^r		X											
Study Treatment ^s		X				X	X						
Local Site Injection Tolerability Assessment ^t		X				X	X						
Tumor Assessments													
CT or MRI Scan ^u	X	Every 8 weeks (±5 days) up to 24 wks, and every 8 or 12 weeks (±5 days) thereafter according to calendar, regardless of treatment delays						X	X (Every 12 weeks)				

Schedule of Activities for Part 2 SC Administration of PF-06801591		Treatment Period						EOT ^{bb}	Post-Treatment			
		Cycle 1 Only (Days 1 to 28)				Cycle 2 (Days 1 to 28)	Subsequent Cycles (Days 1 to 28) ^{aa}		1-Month and Late irAE Follow up ^{cc}			Survival Follow Up ^{dd}
Protocol Activity	Screening ^a (≤28 days prior to study entry)	Day 1	Day 8	Day 15	Day 22	Day 1	Day 1		28 days	90 days	120 days	Every 2 months after 120 day follow up visit
Other Clinical Assessments												
Adverse Events ^v		X	X	X	X	X	X	X	X	X	X	

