Serious Adverse Events ^w	X	X	X	X	X	X	X	X	X	X	X	X Up to 150 days after last treatment
Concomitant Medication and non-drug supportive interventions ^x	X	X	X	X	X	X	X	X	X	X	X	
Subsequent anti-cancer therapy ^y									X	X	X	X
Survival follow up ^{dd}												X
Contraception check ^z	X	X				X	X	X	X	X	X	

BP = blood pressure; CT = computed tomography; ECG = electrocardiogram; ECOG = Eastern Cooperative Oncology Group; EOT = end of treatment; FSH = follicle stimulating hormone; HIV = human immunodeficiency virus; MRI = magnetic resonance imaging; PK = pharmacokinetics; PO = pulse oximetry; TBNK = T cell/B cell/natural killer cell; wks = weeks.

Footnotes for Schedule of Activities for Part 2 Subcutaneous Administration

- Screening:** To be performed within 28 days prior to study entry.
- Informed Consent:** Must be obtained prior to undergoing any study-specific procedures.
- Tumor History:** Will be collected within 28 days during screening prior to study entry. Includes history of disease under study including details of primary diagnosis, treatment history and history of tumor diagnostics.
- Medical History:** Includes history of disease process (eg, staging) other than the cancer under study (active or resolved) and concurrent illness. Includes prior treatments and any current medical treatments for any condition.
- Abbreviated Physical Examination (PE):** Abbreviated PEs should be performed as appropriate at each visit where complete PEs are not required.
- Baseline Signs & Symptoms:** On Day 1 prior to the start of study treatment, patients will be asked about any signs and symptoms experienced within the past 14 days prior to study entry. Baseline signs and symptoms will be recorded on the Medical History CRF page. During the study, any new or worsening conditions since baseline will be recorded on the Adverse Events (AE) CRF page.
- Weight:** Patient's body weight will be measured at Day 1 of each treatment cycle.

- h. **Vital Signs:** includes temperature, sitting BP, pulse rate (to be recorded in the sitting position after 5 minutes of rest), and pulse oximetry (PO, at rest and after exertion). On Day 1 of each cycle, vital signs should be measured prior to infusion start (pre-dose), BP, and pulse rate will be repeated 1 hour (± 10 minutes) after the start of the infusion.
- i. **Performance Status:** Per ECOG performance scale in [Appendix 6](#).

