6.6. Patient Withdrawal

The reason for a patient's discontinuation from treatment will be documented in the end of study/withdrawal CRF. Patients will be followed for at least 120 days after the last dose of study drug for AEs.

Patients may withdraw from treatment at any time at their own request, or they may be withdrawn at the discretion of the investigator or sponsor for safety or behavioral reasons, or the inability of the patient to comply with the protocol-required schedule of study visits or procedures at a given study site.

Reasons for withdrawal of study treatment may include:

- Objective disease progression;*
- Global deterioration of health status requiring discontinuation;
- Unacceptable toxicity;
- Pregnancy;
- Significant protocol violation;
- Lost to follow-up;
- Patient refused further treatment;
- Study terminated by sponsor;
- Death.

*In the case of radiological progression but in the absence of clinical deterioration, if investigator deems it to be in the patient's best interests, the patient will be allowed to stay on study.

Reasons for withdrawal from study follow-up may include:

- Completed study follow-up;
- Study terminated by sponsor;
- Lost to follow-up;
- Refused further follow-up;
- Death.

If a patient does not return for a scheduled visit, every effort should be made to contact the patient. All attempts to contact the patient and information received during contact attempts must be documented in the patient's medical record. In any circumstance, every effort should be made to document patient outcome, if possible. The investigator should enquire about the reason for withdrawal, request the patient to return for a final visit, if applicable, and follow-up with the patient regarding any unresolved AEs.

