8.2. Reporting Period

For SAEs, the active reporting period to Pfizer or its designated representative begins from the time that the patient provides informed consent, which is obtained prior to the patient's participation in the study, ie, prior to undergoing any study-related procedure and/or receiving investigational product, through and including 150 calendar days after the last administration of the investigational product or until administration of subsequent anti-cancer therapy whichever comes first. Death must be reported as an SAE if it occurs within 150 calendar days after last administration of the investigational product, irrespective of any intervening treatment. SAEs occurring to a patient after the active reporting period has ended should be reported to the sponsor if the investigator becomes aware of them. At a minimum, all SAEs that the investigator believes have at least a reasonable possibility of being related to investigational product are to be reported to the sponsor.

If an SAE occurs after informed consent is signed and before study drug is administered, this information will be reported on an SAE Form and will be recorded in the safety database.

AEs (serious and non-serious) should be recorded on the CRF from the time the patient has taken at least 1 dose of investigational product through the patient's last visit. Patients must be followed for AEs for 28 days after the last treatment administration or until all drug related toxicities have resolved, whichever is later; or earlier than 28 days should the patient commence another anticancer therapy in the meantime. Additional, immune-related AEs will be collected with a follow-up phone call at 90 and 120 days after last dose administration date to collect post-treatment related AE information.

If a patient begins a new anticancer therapy, the AE reporting period for non-serious AEs ends at the time the new treatment is started.

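### SAEs and deaths are reportable to day 150 after last dose, but no routine contact for all patients falls between day 127 and day 162, so days 128 to 150 depend on spontaneous, conditional or retrospective reporting

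*Protocol*

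**What the plan says.** Protocol Section 8.2 sets two limits. The active SAE reporting period runs "through and including 150 calendar days after the last administration of the investigational product or until administration of subsequent anti-cancer therapy whichever comes first". Deaths have a stricter rule: "Death must be reported as an SAE if it occurs within 150 calendar days after last administration of the investigational product". That rule holds whatever treatment intervenes.

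The routine contacts after treatment are these:

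- The one-month visit, at days 28 to 35.
- The late immune-related calls of Section 6.4: "Patients will undergo telephone follow-ups at 90 and 120 day", each with a ±7 day window. Section 6.6 matches this: "Patients will be followed for at least 120 days after the last dose of study drug for AEs".
- Survival follow-up under Section 6.5: "To collect OS data, patients will be contacted by telephone every 8 weeks". These calls have a window of one week either way, are counted from the day-120 contact, and go on until the trial ends. The stated purpose is overall survival, with subsequent anti-cancer therapy also recorded.

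The Schedules of Activities (Part 1 IV, Part 1 SC and Part 2) head the survival column "Every 2 months after 120 day follow up visit" and, in the Serious Adverse Events row of that column, enter "Up to 150 days after last treatment".

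**The concern.** The reporting obligation ends at day 150, and the Schedule assigns its last stretch to survival follow-up. Yet the first survival call is due about eight weeks after the day-120 call. If no such call can occur by day 150, the Schedule gives the task to a contact that always comes after the window has closed.

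At stake is how promptly and completely late SAEs and deaths reach the sponsor. Section 8.14.1 starts the 24-hour clock at investigator awareness, so a late contact can mean a late report. Section 9.8 provides no external safety committee, and the internal review depends on what sites report.

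**Working it through.** The plan states no day number for the first survival call, so there is no figure to reproduce. The check is calendar arithmetic on the plan's own intervals, in days after last dose.

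**Inputs.** Reporting limit: day 150 (Protocol 8.2). Last safety call: day 120 ±7 (Protocol 6.4). Survival interval: 8 weeks = 56 days, ±7 (Protocol 6.5), or two months (Schedule column headings). Cut-off for safety tabulations: last dose + 28 days (SAP 6.2.2).

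**1. Day-120 call.** 120 − 7 = 113 to 120 + 7 = 127.

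**2. First survival call.**
- Nominal: 120 + 56 = 176.
- Earliest: 113 + 56 − 7 = 162.
- Latest: 127 + 56 + 7 = 190.
- Counted from nominal day 120 instead of the actual call: 120 + 49 = 169 to 120 + 63 = 183.
- With two months (59 to 62 days): nominal 179 to 182, earliest 113 + 59 − 7 = 165.

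Every variant lies after day 150.

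**3. Lag after the window closes.** 162 − 150 = 12 days at least, 176 − 150 = 26 nominally, 190 − 150 = 40 at most.

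**4. Stretch without routine contact.** No patient can have a routine contact from day 128 to day 161. Inside the window that is 150 − 127 = 23 days, or 23/150 = 15%. For an individual, the time from the actual day-120 call to day 150 is 150 − 127 = 23 to 150 − 113 = 37 days, nominally 30.

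**5. Recall interval for events in days 128 to 150.** Shortest: 162 − 150 = 12 days. Longest: 190 − 128 = 62 days.

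**6. Contacts that only some patients have.**
- Unresolved late immune-related toxicity is followed at least every 4 weeks (Protocol 6.4): 113 + 28 = 141 to 127 + 28 = 155, nominally 148. This covers toxicity already present, not events that begin after the call.
- Patients who stopped for reasons other than progression, death or consent withdrawal have scans every 12 weeks ±1 week (Protocol 7.4). Counting from the end-of-treatment visit (an assumption), the first such scan can fall in days 128 to 150 only if that visit was 128 − 91 = 37 to 150 − 77 = 73 days after last dose. The documents do not fix that interval.
- In Poland (Part 2), women of childbearing potential have a day-150 pregnancy test. It is counted from end of treatment and may be done at home.

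None of these reaches all patients.

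**7. Reach into the analysis.** SAP 6.2.2 tabulates safety data only to last dose + 28 days, or to other anti-cancer therapy if earlier. Days 128 to 150 lie outside that period. The listings include all collected data.

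**The case against.** The strongest reply is that SAE reporting is driven by awareness, not by calls. Sites must report within 24 hours of learning of an event (Section 8.14.1) and are to question each patient about AEs (Section 8.13). The Schedule marks SAEs in the survival phase, and the first survival call can still pick up an event dated by day 150. Deaths are not lost either, since Section 6.6 has sites obtain date and cause. A recall interval of about two months is also accepted elsewhere: day 28 to day 90 is nominally 62 days.

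Most of this stands, and it limits the point to late and recall-dependent ascertainment. A reader might infer that events in the gap are lost, but the documents do not show that. Nor does Section 6.5 forbid asking about SAEs; it states another purpose and leaves the question unmentioned. What the reply does not answer is that the Schedule's own entry has no matching contact before the window closes.

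Two other readings also go too far:

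- That no contact at all falls in days 121 to 150. The day-120 call may itself fall on days 121 to 127, and some patients have the contacts listed above. For the same reason, pairing a day-190 call with a day-121 event to get 69 days of recall fails: a day-190 call implies a day-127 call, which would already have covered day 121.
- That the 150-day limit exists to catch late immune-related events. The amendment summary says it was set to align SAE monitoring with the contraception period; late immune-related assessment runs to day 120.

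**Conclusion.** The point holds as a scheduling gap. The protocol requires reporting to day 150 but sets no routine contact for all patients between day 127 and day 162, and the Schedule's day-150 entry sits in a column whose first call always comes later. The size is 23 days for every patient and 23 to 37 days for an individual, with recall of 12 to about 62 days for events in days 128 to 150. For non-fatal SAEs the reportable stretch is shorter where subsequent anti-cancer therapy starts before day 150; for deaths it is not.

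The effect falls on the SAE safety database, the all-data listings and the internal safety review. A reader might infer under-ascertainment in the Part 2 primary safety results. SAP 6.2.2 rules that out for the tabulations, which stop at last dose + 28 days.

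A reader might also want a count of deaths learned late. The documents do not supply one. As an illustration only, take exponential survival and 23 days = 23/30.44 = 0.756 months. A 12.2-month median (the nivolumab arm in Protocol 1.2.5) gives 1 − exp(−0.693 × 0.756/12.2) = 4.2% of patients alive at day 127 dying in days 128 to 150. An assumed 6-month median gives 8.4%. The first median comes from another drug and another time origin, the second is assumed, and neither shows how many deaths the site would not already know of. The conclusion does not rest on these figures.

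**What to change.** In Protocol Section 6.5 and in the Part 1 and Part 2 Schedules, set the first survival call at day 150 (+7 days) after last dose. At that call, ask about SAEs and death since the day-120 call, then continue every 8 weeks. The one-sided window keeps the call from preceding day 150. In the same edit, reconcile the 8-week interval in the text with the two-month interval in the Schedule headings.

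The cost is one telephone call moved about 176 − 150 = 26 days earlier, at most one extra call per patient over follow-up, and small protocol and CRF wording changes. No treatment rule changes, and the SAP tabulation period can stay as it is.

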6.6. Patient Withdrawal

The reason for a patient's discontinuation from treatment will be documented in the end of study/withdrawal CRF. Patients will be followed for at least 120 days after the last dose of study drug for AEs.

Patients may withdraw from treatment at any time at their own request, or they may be withdrawn at the discretion of the investigator or sponsor for safety or behavioral reasons, or the inability of the patient to comply with the protocol-required schedule of study visits or procedures at a given study site.

Reasons for withdrawal of study treatment may include:

- Objective disease progression;*
- Global deterioration of health status requiring discontinuation;
- Unacceptable toxicity;
- Pregnancy;
- Significant protocol violation;
- Lost to follow-up;
- Patient refused further treatment;
- Study terminated by sponsor;
- Death.

*In the case of radiological progression but in the absence of clinical deterioration, if investigator deems it to be in the patient's best interests, the patient will be allowed to stay on study.

Reasons for withdrawal from study follow-up may include:

- Completed study follow-up;
- Study terminated by sponsor;
- Lost to follow-up;
- Refused further follow-up;
- Death.

If a patient does not return for a scheduled visit, every effort should be made to contact the patient. All attempts to contact the patient and information received during contact attempts must be documented in the patient's medical record. In any circumstance, every effort should be made to document patient outcome, if possible. The investigator should enquire about the reason for withdrawal, request the patient to return for a final visit, if applicable, and follow-up with the patient regarding any unresolved AEs.

All reasonable efforts must be made to locate patients to determine and report their ongoing status. This includes follow-up with persons authorized by the patient as noted above. Lost to follow-up is defined by the inability to reach the patient after a minimum of 2 documented phone calls, faxes, or e-mails as well as lack of response by the patient to 1 registered mail letter. All attempts should be documented in the patient's medical records. If it is determined that the patient has died, the site will use permissible local methods to obtain the date and cause of death. If the investigator's use of a third-party representative to assist in the follow-up portion of the study has been included in the patient's informed consent, then the investigator may use a sponsor-retained third-party representative to assist site staff with obtaining the patient's contact information or other public vital status data necessary to complete the follow-up portion of the study. The site staff and representative will consult publicly available sources, such as public health registries and databases, in order to obtain updated contact information. If, after all attempts, the patient remains lost to follow-up, then the last-known-alive date as determined by the investigator should be reported and documented in the patient's medical records.

If the patient refuses further visits, the patient should continue to be followed for survival unless the patient withdraws consent for disclosure of future information or for further contact. In this case, no further study specific evaluations should be performed, and no additional data should be collected. The sponsor may retain and continue to use any data collected before such withdrawal of consent.

7. ASSESSMENTS

Every effort should be made to ensure that the protocol-required tests and procedures are completed as described. However, it is anticipated that from time to time there may be circumstances, outside of the control of the investigator that may make it unfeasible to perform the test. In these cases the investigator will take all steps necessary to ensure the safety and well-being of the patient. When a protocol-required test cannot be performed, the investigator will document, as soon as possible, the reason and any corrective and preventive actions taken to ensure that normal processes are adhered to. The study team will be informed of these incidents in a timely fashion.

7.1. Safety Assessment

Safety assessments will include collection of AEs, SAEs, vital signs and physical examination, 12-lead ECG, local site injection tolerability assessment (SC administration cohort only), laboratory assessments, including pregnancy tests and verification of concomitant treatments.

7.1.1. Pregnancy Testing or Postmenopausal Status

For female patients of childbearing potential, a serum or urine pregnancy test, with sensitivity of at least 25 mIU/mL and assayed in a certified laboratory will be performed on 2 occasions prior to starting study treatment: once at the start of screening and once at the baseline visit immediately before investigational product administration. Following a negative pregnancy test result at screening, appropriate contraception must be commenced and another negative pregnancy test result will then be required at the baseline visit before the patient may receive the investigational product. Pregnancy tests will also be routinely repeated at every cycle during the active treatment period, at the end of study treatment, at the 28-day Follow-Up visit, and additionally whenever 1 menstrual cycle is missed or when potential pregnancy is otherwise suspected. In the case of a positive human chorionic gonadotropin test, the patient will be withdrawn from treatment but may remain in the study. If a urine test cannot be confirmed as negative (eg, an ambiguous result), a serum pregnancy test is required. In such cases, the participant must be excluded if the serum pregnancy is positive. Additional pregnancy tests may also be undertaken if requested by Investigational Review Boards/Ethics Committees (IRBs/ECs) or if required by local regulations. In Poland only, pregnancy tests should be performed after end of treatment on days 28, 60, 90, 120 and 150. Pregnancy tests on days 60, 90, 120 and 150 may be collected at home by the patient.

For female patients who achieved postmenopausal status and have not experienced their menses since at least 12 consecutive month, a serum FSH test must be conducted at screening only, in order to confirm a FSH level within the laboratory's reference ranges for post menopause.

